#### **4.4.3. Mixed Model for Repeated Measures**

For the continuous efficacy and health outcome variables, data after the occurrence of intercurrent events (including application of any of the censoring rules) will be set to missing. This analysis takes into account both the missingness of data and the correlation of the repeated measurements. This approach assumes that missing observations are missing-at-random (missingness is related to observed data) during the study and borrows information from patients in the same treatment arm taking into account both the missingness of data and the correlation of the repeated measurements. Essentially, this method tries to measure the effect of initially randomized treatments had all patients remained in their randomized treatment throughout the study. For this reason, the MMRM imputation implies a different estimand (hypothetical strategy [ICH 2019]) than the one used for NRI on categorical outcomes.

#### **4.4.4. Hybrid Imputation (Multiple Imputation and Nonresponder Imputation for Categorical Variables; Multiple Imputation and Modified Last Observation Carried Forward for Continuous Variables)**

To determine the effect of missing data due to the COVID-19 pandemic on the clinical trial, a sensitivity analysis will be conducted using hybrid imputation method. The missing data due to the COVID-19 pandemic includes the data collected remotely but considered as “missing” or data which were not collected due to the COVID-19 pandemic (i.e., some efficacy assessments are not to be collected at the remote visits or the whole visit was missed due to pandemic).

For the binary endpoints, the hybrid method will impute the missing data due to COVID-19 by multiple imputation (MI) whereas other missing data not due to COVID-19 by NRI. This imputation procedure addresses the hybrid estimand assuming that the effects of treatments will be the same had patients not experienced any intercurrent event related to COVID-19 (e.g., either remote visits or missed visits due to COVID-19, etc.) or the effect will disappear after any intercurrent event not related to COVID-19. Specifically, the algorithm is as follows:

1. Identify all missing data (including the missing data due to COVID-19 and not due to COVID-19).
2. Implement the MI to impute all missing data and generate  $m$  imputed complete data sets.
3. Identify the missing data due to COVID-19 and not due to COVID-19 in the original data set.
4. For each of these  $m$  imputed complete data sets from Step 2, the imputed data for missing data not due to COVID-19 will be replaced by NRI and all other data including imputed or observed will be used to derive the binary outcome.

For the continuous endpoints, the hybrid method will impute the missing data due to COVID-19 by MI whereas other missing data not due to COVID-19 by mLOCF. This imputation procedure addresses the hybrid estimand assuming that the effects of treatments will be the same had patients not experienced any intercurrent event related to COVID-19 (e.g., either remote visits or missed visits due to COVID-19, etc.) or will remain the same after the event that caused missing data not due to COVID-19 as it was just prior to the missing data event. Specifically, the algorithm is as follows:

1. Identify all missing data (including the missing data due to COVID-19 and not due to COVID-19).
2. Implement the MI to impute all missing data and generate  $m$  imputed complete data sets.
3. Identify the missing data due to COVID-19 and not due to COVID-19 in the original data set.
4. For each of these  $m$  imputed complete data sets from Step 2, the imputed data for missing data not due to COVID-19 will be set as missing again and imputed by mLOCF.

The sensitivity analysis aforementioned will be performed on the primary and key secondary endpoints. The number of imputed data sets will be  $m=100$  and a 6-digit seed value will be pre-

specified for each analysis. Within the program, the seed will be used to generate the  $m$  seeds needed for imputation. The initial seed values are given below:

**Table JAHO.4.2. Seed Values for Multiple Imputation**

Analysis	Seed value
Proportion of patients achieving $SALT \leq 20$ at Weeks 16, 24, 36	123450
Proportion of patients achieving a PRO for Scalp Hair Assessment 0 or 1 with a $\geq 2$ -point improvement from Baseline at Week 36	123451
Proportion of patients achieving an absolute SALT score $\leq 10$ at Weeks 24 and 36	123450
Proportion of patients achieving $SALT_{90}$ at Week 36	123450
Proportion of patients achieving $SALT_{50}$ at Week 12	123450
Percent change from Baseline in SALT score at Week 36	123450
Proportion of patients achieving ClinRO Measure for EB Hair Loss 0 or 1 with $\geq 2$ -point improvement from Baseline at Week 36	123452
Proportion of patients achieving ClinRO Measure for EL Hair Loss 0 or 1 with $\geq 2$ -point improvement from Baseline at Week 36	123453

Abbreviations: ClinRO = clinician-reported outcome; EB = eyebrow; EL = eyelash; PRO = patient-reported outcome; SALT = Severity of Alopecia Tool;  $SALT_{50}$  = at least 50% improvement from Baseline in SALT score;  $SALT_{90}$  = at least 90% improvement from Baseline in SALT score;

Analysis: A logistic regression or analysis of covariance (ANCOVA) will be applied, as appropriate, on each imputed data set. Details about logistic and ANCOVA models can be found in Section 4.2.3. The final inference on treatment difference is conducted from the multiple data sets using Rubin's combining rules, as implemented in SAS® PROC MIANALYZE.

#### **4.4.5. Hybrid Imputation for Week 104 DBL**

A similar hybrid imputation will be applied to the efficacy analysis at the Week 104 DBL.

For the binary endpoints, the hybrid method will impute the data collected at remote visits due to COVID-19 pandemic or any intermittent missing data or automatic discontinuation at Week 76 by IWRS if applicable by multiple imputation (MI) whereas other missing data by NRI. This imputation procedure addresses the hybrid estimand assuming that the effects of treatments will be the same had patients not experienced any intercurrent event related to COVID-19 or intermittent missing or automatic discontinuation at Week 76 by IWRS if applicable, or the effects will disappear after any other intercurrent event. The imputation algorithm will be similar to this outlined in Section 4.4.3.

For the continuous endpoints, the hybrid method will impute the data collected at remote visits due to COVID-19 pandemic or any intermittent missing data or automatic discontinuation at Week 76 by IWRS if applicable by multiple imputation (MI) whereas other missing data by mLOCF. This imputation procedure addresses the hybrid estimand assuming that the effects of treatments will be the same had patients not experienced any intercurrent event related to

COVID-19 or intermittent missing or automatic discontinuation at Week 76 by IWRS if applicable, or the effects will remain the same after the event that caused missing data due to other reasons as it was just prior to the missing data event. The imputation algorithm will be similar to this outlined in Section 4.4.3.

The number of imputed data sets will be  $m=100$  and a 6-digit seed value will be pre-specified for each analysis. Within the program, the seed will be used to generate the  $m$  seeds needed for imputation. The initial seed values are given below:

**Table JAHO.4.3      Seed Values for Imputation**

Analysis	Seed value
SALT related endpoints ( $SALT \leq 20$ , $SALT \leq 10$ , $SALT_{90}$ , $SALT_{50}$ , etc.)	123450
PRO for Scalp Hair Assessment endpoints	123451
ClinRO Measure for EB Hair Loss endpoints	123452
ClinRO Measure for EL Hair Loss endpoints	123453
HADS related endpoints	123454
Skindex-16 Adapted for AA endpoints	123455
EQ-5D-5L endpoints	123456
SF-36 endpoints	123457

#### 4.4.6. Tipping Point Analyses

To investigate the missing data mechanism, an additional analysis using multiple imputation (MI) under the missing not at random assumption will be provided for the primary objective, which compares the proportion of patients achieving  $SALT \leq 20$  of Baricitinib 4-mg and 2-mg doses and placebo at Week 36. The tipping point analysis may also be used as an additional analysis for some key secondary objectives.

All patients in the full analysis set (FAS) population are included. Data after the occurrence of intercurrent events (including application of any of the censoring rules) will be set to missing. Within each analysis, the most extreme case will be considered, in which all missing data for patients randomized to baricitinib doses will be imputed using the worst possible result, and all missing data for patients randomized to placebo will be imputed with the best possible result. Treatment differences will be analyzed using logistic regression or analysis of covariance (ANCOVA), as appropriate.

For continuous variables, the following process will be used to determine the tipping point:

1. To handle intermittent missing visit data, a Markov chain Monte Carlo method (SAS® Proc MI with MCMC option) will be used to create a monotone missing pattern.
2. A set of Bayesian regressions (using SAS® Proc MI with MONOTONE option) will be used for the imputation of monotone dropouts. Starting from the first visit with at least 1 missing value, the regression models will be fit sequentially with treatment as a fixed effect and values from the previous visits as covariates.
3. A delta score is added to all imputed scores at the time point where the analysis is conducted for patients in the baricitinib treatment groups, thus, worsening the imputed value. The delta score is capped for patients, based on the range of the outcome measure being analyzed.
4. Treatment differences between baricitinib and placebo are analyzed for each imputed data set using ANCOVA. Results across the imputed data sets are aggregated using SAS® Proc MIANALYZE in order to compute a p-value for the treatment comparisons for the given delta value.
5. Steps 3 and 4 are repeated, and the delta value added to the imputed baricitinib scores is gradually increased. The tipping point is identified as the delta value which leads to a loss of statistical significance (aggregated p-value  $>0.05$ ) when evaluating baricitinib relative to the placebo group.

As a reference, for each delta value used in Steps 3-5, a fixed selection of delta values (ranging from slightly negative to slightly positive) will be added to imputed values in the placebo group, and Step 4 will be performed for the combination. This will result in a 2-d table for each time point of interest, with the columns representing the delta values added to the imputed placebo responses, and the rows representing the delta values added to the imputed baricitinib responses. Separate 2-d tables will compare each baricitinib dose group to placebo.

A similar process will be used for the categorical variables:

1. Missing responses in the baricitinib groups will be imputed with a range of low response probabilities, including probabilities of 0, 0.1, and 0.2.
2. For missing responses in the placebo group, a range of response probabilities will be used to impute the missing values. Multiple imputed data sets will be generated for each response probability.
3. Treatment differences between baricitinib and placebo are analyzed for each imputed data set using logistic regression. Results across the imputed data sets are aggregated using SAS® Proc MIANALYZE in order to compute a p-value for the treatment comparisons for the given response probability. If the probability values do not allow for any variation between the multiple imputed data sets (e.g., all missing responses in the placebo and baricitinib groups are imputed as responders and nonresponders, respectively), then the p-value from the single imputed data set will be used.

The tipping point is identified as the response probability value within the placebo group that leads to a loss of statistical significance when evaluating baricitinib relative to placebo.

For tipping point analyses the number of imputed data sets will be  $m=100$  and the seed value to start the pseudorandom number generator of SAS Proc MI (same values for MCMC option and for MONOTONE option) will be as specified in [Table JAHO.4.4](#).

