### 4.2. General Considerations

This plan describes *a priori* statistical analyses for efficacy, health outcomes, and safety that will be performed.

Statistical analysis of this study will be the responsibility of Eli Lilly and Company (Lilly). The statistical analyses will be performed using SAS® Version 9.4 or a more recent version.

Not all displays described in this SAP will necessarily be included in the CSR. Not all displays will necessarily be created as a “static” display. Some may be incorporated into interactive display tools instead of or in addition to a static display. Any display described in this SAP and not included in the CSR would be available upon request.

Statistical tests of treatment effects and confidence intervals (CIs) will be performed at a 2-sided significance level of 0.05, unless otherwise stated (e.g., graphical multiple testing strategy in Section 4.6).

Data collected at early termination visits will be mapped to the closest scheduled visit number for that patient if it falls within the visit window as discussed in Section 4.2.2. For by-visit summaries, only visits in which a measure was scheduled to be collected will be summarized. Any unscheduled visit data will be included at the patient-level listings. However, the data may still be used in other analyses, including but may not be limited to, shift analyses for safety analyses, change from baseline using modified last observation carried forward (mLOCF) for efficacy analyses, and other categorical analyses including safety.

This SAP also covers the Addendum 4 safety data up to week 248 which will be analyzed in the final database lock (F-DBL). As part of Addendum 4, implemented in Mexico, patients were permitted to continue treatment beyond Week 200, extending until Week 248.

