## 4.6. Multiple Comparisons/Multiplicity

This study uses an operationally seamless adaptive Phase 2/3 study design. Data collected from the approximately 200 Phase 3 patients enrolled during the Stage 1 randomization scheme and all patients enrolled during Stage 2 randomization scheme will remain blinded, and the FAS population will be used for the primary efficacy analysis. Pre-specified changes in randomization ratio and allocation to selected doses into Stage 2 will be triggered only through IWRS. Hence, the Type I error rate for the primary efficacy analysis is controlled at a 2-sided alpha level of 0.05.

Multiplicity adjusted analyses will be performed on the primary and key secondary objectives using the FAS population in order to control the overall familywise Type I error rate at a 2-sided alpha level of 0.05. The graphical multiple testing procedure described in Bretz et al. (2011) will be used. The graphical approach is a closed testing procedure; hence, it strongly controls the familywise error rate across all endpoints (Alosh et al. 2014). [Figure JAHO.4.1](#) illustrates the graphical testing procedures that will be used. The primary endpoint for both doses will be first tested at a two-sided  $\alpha=0.025$ . If neither of the null hypotheses is rejected, no further testing is conducted, as the  $\alpha$  for that test is considered “spent” and cannot be passed to other endpoints. If at least one of null hypotheses is rejected, the testing process continues, with the remaining  $\alpha$  propagated according to the weights on the corresponding edges displayed in [Figure JAHO.4.1](#). The testing process continues as long as there is at least one hypothesis in the scheme that can be rejected at its allocated  $\alpha$  level at that point. Each time a hypothesis is rejected, the graph is updated to reflect the reallocation of  $\alpha$ , which is considered “recycled” by Alosh et al. (2014). This iterative process of updating the graph and reallocating  $\alpha$  is repeated until all hypotheses have been tested or when no remaining hypotheses can be rejected at their corresponding  $\alpha$  levels.

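### SAP 4.4.6 does not tie the tipping-point cut-off to the alpha at which each dose is tested (0.025 initially), so robustness to missing data can be overstated

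*SAP*

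**What the plan says.** The point concerns the randomised Phase 3 comparison in the SAP. The open-label addendum protocol has descriptive objectives only.

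- **SAP 4.4.6, continuous variables.** The steps open with "For continuous variables, the following process will be used to determine the tipping point". Step 5 sets the cut-off: "The tipping point is identified as the delta value which leads to a loss of statistical significance (aggregated p-value $>0.05".
- **SAP 4.4.6, categorical variables.** The text continues "A similar process will be used for the categorical variables" and ends "The tipping point is identified as the response probability value within the placebo group that leads to a loss of statistical significance". No level is given.
- **SAP 4.4.6, unit of comparison.** "Separate 2-d tables will compare each baricitinib dose group to placebo". This sentence stands with the delta tables of the continuous process.
- **SAP 4.6.** "The primary endpoint for both doses will be first tested at a two-sided" alpha of 0.025. Alpha is reallocated after each rejection, and the family-wise level is 0.05. The edge weights are in Figure JAHO.4.1, which is not reproduced in the text available.
- **SAP 4.2.** "Statistical tests of treatment effects and confidence intervals (CIs) will be performed at a 2-sided significance level of 0.05, unless otherwise stated", with the graphical strategy of Section 4.6 given as the example of an exception.
- **Which analysis is committed.** The one planned tipping-point analysis is for SALT ≤ 20 at Week 36 (Tables JAHO.4.4, 4.5 and 4.7). For key secondary objectives it is optional. Section 4.11.3 lists it among the supplementary analyses meant to show robustness.

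**The concern.** A tipping-point analysis asks how unfavourable the missing outcomes must be before the study's conclusion fails. For each dose that conclusion is a rejection at the level assigned in Section 4.6, not a stand-alone 5% test. The only number attached to loss of significance in Section 4.4.6 is 0.05. The categorical process uses the same phrase and is described as similar, so a programmer could easily carry 0.05 over.

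Scenarios with p between 0.025 and 0.05 would then be reported as surviving although the hypothesis would not be rejected at its initial level. The same mismatch arises if the optional analysis is run on percent change in SALT at Week 36. That is a continuous key secondary endpoint whose level also comes from the graph. At stake is how far the Week 36 result is described as robust to missing data.

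**Working it through.** **Inputs.** SAP 4.1: up to 625 Phase 3 patients, 2:2:3 allocation, and response rates of 5% (placebo), 20% (2-mg) and 30% (4-mg). 625 × 2/7 ≈ 179, so the arms are 179, 179 and 267. SAP 4.4.6: missing baricitinib responses imputed at low probabilities including 0, with m = 100 imputations. The SAP gives no missing rate, so the rates below are assumptions, taken as equal across arms.

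**The plan's own figure.** Section 4.1 states more than 90% power with a two-sided Fisher exact test at 0.04 (4-mg) and 0.01 (2-mg) under the original scheme. Exact enumeration gives >99.9% and 96.1%, so the statement reproduces. At 0.025 each, power is >99.9% and 98.3%.

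**The levels.** 0.025 + 0.025 = 0.05, the family-wise level. The critical |z| is 2.241 at 0.025 and 1.960 at 0.05. No local level in the graph can exceed 0.05, so a fixed 0.05 either equals the confirmatory level or is more lenient.

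**Formulas.** Let f be the missing fraction, n the arm size, p_b the planned baricitinib rate, and q the response probability imputed to missing placebo patients. Missing baricitinib patients are counted as nonresponders.

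- Baricitinib rate: e_b = (1 − f)·p_b
- Placebo rate: e_p = (1 − f)·0.05 + f·q
- Within-imputation variance of the log odds ratio: W = 1/[n_b·e_b(1 − e_b)] + 1/[n_p·e_p(1 − e_p)]
- Between-imputation variance: B = f·n_p·q(1 − q)/[n_p·e_p(1 − e_p)]²
- Total variance: T = W + 1.01·B
- z = [logit(e_b) − logit(e_p)]/√T

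q is raised in steps of 0.005 until p exceeds the cut-off. This approximates the planned logistic regression combined over imputations.

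**Worked case: 2-mg, 10% missing.** e_b = 0.9 × 0.20 = 0.18.

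- q = 0.450: e_p = 0.045 + 0.045 = 0.090; difference in logits 0.797; W = 0.1061, B = 0.0206, T = 0.1269; z = 2.238, p = 0.0252. This is the tip at 0.025.
- q = 0.500: e_p = 0.095; z = 2.113, p = 0.035. Lost at 0.025, still significant at 0.05.
- q = 0.565: e_p = 0.1015; difference 0.664; W = 0.0991, B = 0.0165, T = 0.1158; z = 1.952, p = 0.0509. This is the tip at 0.05.

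**Results: placebo response probability at the tip.**

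| Dose | Assumed missing | Read at 0.05 | Read at 0.025 | Shift |
|---|---|---|---|---|
| 2-mg | 5% | none | none | – |
| 2-mg | 10% | 0.565 | 0.450 | 0.115 |
| 2-mg | 15% | 0.325 | 0.255 | 0.070 |
| 4-mg | 5% | none | none | – |
| 4-mg | 10% | none | none | – |
| 4-mg | 15% | 0.870 | 0.780 | 0.090 |

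At 5% missing, even with every missing placebo patient a responder (q = 1), 2-mg gives p = 0.014. For 4-mg at 10% missing the same extreme gives p = 0.002.

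**Cross-check.** A pooled two-proportion z-test with whole patients (179/179/268), adding missing placebo patients as responders one at a time, gives:

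- 2-mg, 10% missing: 12/18 = 0.67 at 0.05 against 10/18 = 0.56 at 0.025.
- 2-mg, 15% missing: 10/27 = 0.37 against 8/27 = 0.30.
- 4-mg, 15% missing: 24/27 = 0.89 against 22/27 = 0.81.

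The tipping values depend on the method. The shifts are similar, 0.07 to 0.11.

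**The case against.** The strongest reply is that a reader might infer that the SAP reads the primary tipping point at 0.05, and it does not say so. The printed 0.05 belongs to the continuous steps, while the committed analysis is binary and has no stated level. Section 4.2 names the Section 4.6 strategy as an exception to the 0.05 default, so loss of significance for the primary hypotheses could already mean loss at the Section 4.6 level. This stands. It turns the point from a wrong level into an unstated one for the primary endpoint. An unstated level still needs fixing when the only number nearby is 0.05.

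Second, Section 4.11.2 says that analyses outside the primary and key secondary objectives are not adjusted for multiplicity, so a nominal 0.05 could be called a declared convention. That does not settle the matter. An analysis offered as evidence that the primary conclusion is robust should ask when that conclusion fails.

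Third, 0.025 is only the initial level. Recycling may raise it, and without the figure nobody can check how far. This stands, and the fix allows for it.

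Fourth, the practical effect is limited. At 10–15% missing, a tip needs missing placebo patients to respond at 0.255 or more even at the stricter cut-off, about five times the planned 5%. Section 4.4.6 also requires the most extreme case to be examined. This is fair: the description of robustness would often stay the same.

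**Conclusion.** The point holds in conditional form. Section 4.4.6 fixes 0.05 for continuous variables, gives no other level for the binary primary endpoint, and does not refer to the level in Section 4.6. If 0.05 is used, robustness can be overstated and is never understated.

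The 0.07 to 0.12 shift rests on the planning response rates, an assumed 10–15% missing equally in all arms, missing baricitinib patients counted as nonresponders, and a normal approximation to the planned model.

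Two stronger conclusions might be inferred, and the documents support neither. One is that reported robustness is in fact overstated. That would require 0.05 to have been applied, enough missing data for a tip, and a local level still below 0.05. The other is that false-positive control is weakened. The tipping point makes no rejection decision, and the primary test keeps its Section 4.6 level, so the rate at which a 0.05 read-off would reject under the null is beside the point.

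**What to change.** In SAP 4.4.6, replace the fixed 0.05 in step 5 with the alpha level at which that dose's hypothesis was tested in the graphical procedure of Section 4.6: 0.025 per dose for the primary endpoint before any recycling, or the recycled level where it applies. State that the same rule governs the categorical algorithm.

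The current SAP version precedes only the final database lock, and its predecessor was approved before the Week 36 primary lock. For the Week 36 analysis this therefore means re-reading p-values already produced at the stated cut-off and reporting which level was used. No new imputations or models are needed. The cost is one sentence and a changed read-off. The downside is that the reported tipping point may become slightly less favourable.
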